thyroid ultrasound is of uncertain value for early detection of MTC in patients

- o Acute Pancreatitis: Discontinue promptly if pancreatitis is suspected since it may be life-threatening. Do not restart if pancreatitis is confirmed.
- Acute Gallbladder Disease: If cholelithiasis or cholecystitis are suspected.
- Serious hypoglycemia: Can occur when Saxenda® is used with an insulin secretagogue (eg, sulfonylureas). Consider lowering the dose of anti-diabetic drugs
- Heart rate increase: Monitor heart rate at regular intervals. Discontinue Saxenda® if patients experience a sustained increase in resting heart rate.
- Renal impairment: Has been reported postmarketing, usually in association with nausea, vomiting, diarrhea, or dehydration which may require hemodialysis. Use caution when initiating or escalating doses of Saxenda® in patients with renal
- Hypersensitivity reactions: Postmarketing reports of serious hypersensitivity reactions (e.g., anaphylactic reactions and angioedema). Discontinue Saxenda® and other suspect medications and promptly seek medical advice.
- Angioedema has been reported with other GLP-1 receptor agonists. Use caution in a patient with a history of angioedema with another GLP-1 receptor agonist because it is unknown whether such patients will be predisposed to angioedema with Saxenda®.
- Suicidal behavior and Ideation: monitor for depression or suicidal thoughts. Discontinue Saxenda® if symptoms develop.

Most common adverse reactions, reported in greater than or equal to 5% are: nausea, hypoglycemia, diarrhea, constipation, vomiting, headache, decreased appetite, dyspepsis, fatigue, dizziness, abdominal pain, and increased lipase.

U.S. Food and Drug Administration's Pregnancy Category: Category X (All

The brand name Saxenda®, which is indicated as an adjunct to diet and exercise for chronic weight management in overweight or obese patients, has a pregnancy category of X. Saxenda® is contraindicated in all pregnant women, including those who are already overweight or obese, because weight loss may result in fetal harm. If a woman becomes or wishes to become pregnant while on Saxenda®, discontinue treatment.

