476 will be discontinued after consulting with the subject's primary physician/endocrinologist. 477 Patients taking an insulin secretagogue (eg, sulfonylureas) will be informed of the 478 increased risk of hypoglycemia associated with co-administration of the study drug 479 and instructed to notify the investigators of any symptoms of hypoglycemia. 480 If the subject is a female of childbearing potential (sexually active and not sterile nor 481 postmenopausal for at least 1 year), have a negative pregnancy test within 4 weeks 482 prior to study commencement, and then at 3, 6, and 9 months. 483 Use of reliable contraception will be assessed during the study period. 484 DSMB reviews all AEs including SAEs and provides the appropriate 485 recommendations 486 487 1.6.2 **Potential benefits** It is hypothesized that this study drug will help the subject lose weight and decrease the incidence 488 or severity of weight related co-morbidities. In addition, the medical community and society 489 490 stand to benefit from a better understanding of the efficacy and safety of the study drug post-RYGB. 491 2 492 **Study Objectives** 493 2.1 **Primary Objective** 494 The primary objective of this study is to assess the utility of liraglutide to reverse weight regain versus placebo in patients at least 18 months following RYGB who are experiencing weight regain. 495 496 2.2 **Secondary Objective** The secondary objectives of this study are to assess the efficacy of liraglutide in improving 497 cardiometabolic risk profile (as indicated by serum lipids, HbA1c, and waist circumference) and quality 498 of life (as assessed by PHO-9 (Patient Health Questionnaire), versus placebo in patients at least 18 499 months following RYGB who are experiencing weight regain, as well as the safety of liraglutide in this 500 patient population. 501 3 **Study Design** 502 503 3.1 **Research Design and Methods** The specific aims of this proposal are: 504 To evaluate the effects of liraglutide on body weight loss in patients who are experiencing weight 505 506 regain following RYGB. We will perform a randomized, double-blinded, placebo-controlled trial of liraglutide 507 versus placebo over a follow-up period of 12 months. 508 We hypothesize that the liraglutide group will contain a significantly greater 509 proportion of patients achieving at least 5% loss of pre-randomization body 510 weight at 12 months, than the placebo group. 511 To evaluate the effects of liraglutide on cardiometabolic risk and quality of life in patients who 512 are experiencing weight regain following RYGB. 513 We will perform a randomized, double-blinded, placebo-controlled trial of liraglutide 514 515 versus placebo over a follow-up period of 12 months.

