579 580 581 582 583 584 585 586 587 588	4.2 Rationale for study population The Roux-en-Y gastric bypass (RYGB) is not only the most common bariatric procedure, but also the gold standard to which all others are compared. The average weight loss after RYGB is approximately 35% total body weight. However, the majority of patients who undergo this procedure experience weight regain and thus are at risk of, or re-acquire co-morbid conditions, such as Type 2 diabetes mellitus or hypertension. Revisional surgery, which is the most common treatment for weight regain after bariatric surgery, is often thwarted by resistance from insurance companies, leaving patients with only diet and behavioral change as an option. Due to the fact the GLP-1 agonism plays a significant role in weight loss after RYGB, liraglutide is thought to be a promising adjunct to the long-term treatment plan in patients who experience weight regain after RYGB.
589	4.3 Inclusion Criteria
590 591 592 593 594 595 596	 >18 years who are deemed medically stable ≥18 months status-post RYGB at time of enrollment BMI of ≥30 kg/m² or ≥ 27 kg/m² in the presence of at least one weight-related comorbid condition Regain of ≥10% of maximum TBWL post-RYGB Ability to provide informed consent before any trial-related activities Express willingness to provide signed informed consent and follow protocol requirements
597	4.4 Exclusion Criteria
598	• BMI of $>45 \text{ kg/m}^2$

• Pregnancy at time of enrollment

600

604

605 606

607

608

609

610

613

614

622

623

624

625

626 627

628

629 630

631

632 633

634

635 636

637

638

639

640 641

642

643

644

645

- Intention of becoming pregnant or breast feeding in the next 12 months
- Females of childbearing potential who are not using adequate contraceptive methods
- Presence of acute psychiatric problems or immaturity which would compromise cooperation with the study protocol
 - Presence of biliary disease
 - Known or suspected allergy to liraglutide or any product components
 - Personal or family history of medullary thyroid carcinoma or multiple endocrine neoplasia syndrome type 2
 - History of pancreatitis
 - History of alcoholism
 - History of Type 1 DM (Diabetes Mellitus)
- History of previous bariatric surgery other than RYGB except h/o LAGB and band removal.
- >10 years status-post RYGB
 - < 25% TBWL at post-RYGB weight nadir
 - >50% post-operative TBWL at time of screening
- Simultaneous use of any weight loss medications

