5.3 Subject Compliance Monitoring

- The study drug will be dispensed to each subject at study visits (baseline, 3, 6, 9 months) and will be recorded by the investigational pharmacy and study team.
 - The subjects are required to return used pens when receiving new drug and the number of used pens returned will be recorded by the investigational pharmacy.
 - Subjects are required to bring a daily study drug administration log to 3, 6, 9, and 12 months study visits.
 - Subjects who are not compliant with administrating the study drug ≥ 30 days will be withdrawn from the study.

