5.6.3 Return or Destruction of Study Drug

At the completion of the study, there will be a final reconciliation of drug shipped, drug consumed, and drug remaining. This reconciliation will be logged on the drug reconciliation form, signed and dated. Any discrepancies noted will be investigated, resolved, and documented prior to return or destruction of unused study drug. Drug destroyed on site will be documented in the study files.

6 Study Procedures

Visit Number	1			2			3			4			5
	Baseline	1M	2M	3 months	4M	5M	6 months	7M	8M	9 months	10M	11M	12 months
Visit window	0-4 wks prior to the treatment			± 4 wks			± 4 wks			± 4 wks			± 4 wks
Informed consent	X												
Screening	X												
Demographics	X												
Medical History	X												
Weight, BP, HR, Waist & Neck Circumference	X			X			X			X			X
Height	X												
Medications	X			X			X			X			X
Blood Pregnancy Test (Beta Quantitative HCG) (Only applicable for women of childbearing potential)	X			X			X			X			X
¹ BMP, HbA1c, ¹ Lipid profile, Amylase, Lipase	X			X			X			X			X
Additional plasma and	X						X						X

serum for future analyses													
PHQ-9, IPAQ, 24 hr diet recall	X			X			X			X			X
Diet and Physical Activity Counseling by RD	X			X			X			X			X
Body Composition	X			X			X			X			X
Comorbidities: Diabetes, Hypertension, STOP-BANG	X			X			X			X			X
² AEs	X	X	X	X	X	X	X	X	X	X	X	X	X
Study Medication Compliance Phone call		X	X		X	X		X	X		X	X	

795

796

804

807

810 811

- 1. Fasting is required
- 2. Ask about hypoglycemia symptoms for patients with Type 2 DM

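### Pregnancy is excluded without qualification, but the hCG test that checks it is limited to women defined as sexually active, and the passages on test timing do not agree

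*Combined protocol and SAP*

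**What the plan says.** **The exclusion.** Section 1.2.8 lists pregnancy as a contraindication, and Section 1.2.10 states "Saxenda® is contraindicated in all pregnant women". Section 1.6.1 offers, as a risk measure, that every contraindication is among the exclusion criteria. Section 4.4 accordingly lists "Pregnancy at time of enrollment", with no subgroup attached.

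**The check.** The pregnancy test is restricted to women of childbearing potential in Sections 3.7.1, 6.1.7 and 6.2.4, in the Section 6 schedule, and in Attachment 1. The contraception exclusion in Section 4.4 uses the same term. It is defined only in Section 1.6.1: "If the subject is a female of childbearing potential (sexually active and not sterile nor", followed by postmenopausal status of at least one year.

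**The timing.** For the women it covers, Section 1.6.1 requires that they "have a negative pregnancy test within 4 weeks" "prior to study commencement, and then at 3, 6, and 9 months". Section 6 places the baseline visit "0-4 wks prior to the treatment", gives each later visit a window of plus or minus 4 weeks, and marks the test at baseline and at 3, 6, 9 and 12 months. Section 4.5.2 counts a subject as enrolled on signing consent, and Section 4.5.1 allows no screening test before that signature.

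**The concern.** An exclusion is only as good as the check behind it. Here the exclusion applies to every pregnant woman, while the only laboratory check applies to a narrower group. The contraception criterion is no backstop, because it uses the same term and so misses the same women.

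The condition that narrows the group is also a weak proxy. It is in the present tense and has no look-back period, whereas pregnancy at consent depends on the preceding weeks. The protocol does not say how sexual activity is to be established.

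What is at stake is subject safety at entry. Section 1.2.10 gives the drug pregnancy category X and reports fetal abnormalities in rats and rabbits, in rabbits at exposures below the human one. The sample size and the primary analysis are not affected.

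**Working it through.** The documents give no figure to reproduce on this point. The check sets the passages side by side and then does date arithmetic on the visit windows.

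**Step 1: who is excluded and who is tested.** Under Section 1.6.1 a woman has childbearing potential only if all three conditions hold: sexually active, not sterile, and not postmenopausal for a year or more. Taking the groups in turn:

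- Sterile, or postmenopausal for at least a year: not tested. Pregnancy is not a practical possibility, so nothing is lost.
- Not sterile, not postmenopausal for a year, sexually active: tested, and contraception required.
- Not sterile, not postmenopausal for a year, judged not sexually active: no required test and no contraception criterion. The exclusion in Section 4.4 still applies to her.

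The third group is the gap between exclusion and check.

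**Step 2: age of the baseline test at first dose.** Section 6 allows baseline 0 to 4 weeks before treatment, and 4 × 7 = 28 days. No test is scheduled on the day of first dose, so a negative result may be 0 to 28 days old.

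**Step 3: interval between scheduled tests.** Take 3 months as 365.25 / 4 ≈ 91 days.

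- First dose to the month-3 test: nominally 91 days (13 weeks), at most 91 + 28 = 119 days (17 weeks).
- Baseline test to the month-3 test: at most 28 + 91 + 28 = 147 days (21 weeks).
- Between two consecutive follow-up tests, the first done 28 days early and the second 28 days late: 28 + 91 + 28 = 147 days, the same limit.

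**Step 4: anchor dates.**

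- Section 1.6.1 counts its 4 weeks back from study commencement, which is not defined. If that means first dose, it agrees with Section 6. If it means consent, no study test could satisfy it, because Section 4.5.1 bars testing before consent.
- Section 4.4 judges pregnancy at enrollment, which Section 4.5.2 equates with consent. Read literally, that moment comes before any study test.
- Section 1.6.1 stops testing at 9 months; Section 6 adds a test at 12 months.

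**The case against.** The best defence is that the protocol has several layers. Section 1.6.1 says that use of reliable contraception will be assessed during the study, without limiting this to a subgroup. Section 6.2.6 says pregnancies will be monitored throughout, Section 6.2.7 adds contact in the months between visits, and Section 8.2.1.5 stops the drug on pregnancy. Outside Section 1.6.1 the term childbearing potential carries no qualifier, so a site might well test more widely. Women who are truly not sexually active are also unlikely to be pregnant.

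Much of this stands, and it limits the point. It does not close the gap at entry: monitoring and stopping depend on a pregnancy being noticed, and wider testing would be a site's choice rather than something the plan requires.

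Several stronger readings are tempting, but the documents do not support them:

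- *That drug may be released before the hCG result.* Section 5.3 says "The study drug will be dispensed to each subject at study visits (baseline, 3, 6, 9 months", and the sample is taken at that same baseline visit. But Section 1.6.1 requires a negative test in the women it covers, Section 4.5.1 requires evidence that all criteria are met, and Section 5.6.1 randomises only eligible subjects.
- *That an untested woman can never be tested later.* Nothing in Section 6 fixes childbearing status at baseline. A woman whose status changes comes within the definition at her next visit, provided someone re-rates her. No passage requires that re-rating.
- *That a conception after a negative test breaches the exclusion.* It does not, because she was not pregnant at enrollment. The interval in Step 2 is a matter of timing, not an eligibility failure.
- *That the intention criterion is materially too short.* It reads "Intention of becoming pregnant or breast feeding in the next 12 months", and 12 months of dosing may begin up to 4 weeks after it is assessed. The shortfall is at most about 4 weeks at the end of dosing, in a self-reported criterion with other safeguards alongside it, and is too small to pursue.

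**Conclusion.** The point holds in this form. Following the plan as written, a non-sterile, premenopausal woman judged not sexually active meets the pregnancy exclusion without an hCG test at baseline, and has none later unless she is re-rated. That rests on taking the Section 1.6.1 parenthesis as the working definition, and the documents offer no other.

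The number affected cannot be estimated from the documents. Any headcount would be assumption throughout, and would count untested women rather than pregnant ones. The number of pregnancies missed is likely to be small.

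The timing inconsistency is separate and secondary. The limits of 28 days and about 147 days are extremes of the stated windows, not typical values, and the second concerns scheduled tests only. Whether those intervals are acceptable is a clinical judgement for the sponsor. The statistical review can say only that the passages use different anchors and different test lists. The correction is worth making because it closes a definable safety gap at very little cost.

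**What to change.** 1. Reconcile the definition in Section 1.6.1 with Sections 1.2.8, 1.2.10 and 4.4, and with the statement in Section 1.6.1 that all contraindications are exclusions. The hCG already scheduled at each visit should cover every woman to whom the pregnancy exclusion can apply, so the sexual-activity qualifier should not narrow who is tested. State separately whether the contraception criterion keeps its present scope.
2. Reconcile the timing passages: define study commencement in Section 1.6.1; state how an exclusion judged at enrollment (Sections 4.4 and 4.5.2) relates to a test taken after consent and up to 4 weeks before treatment (Section 6); and bring the test list in Section 1.6.1 (3, 6 and 9 months) and the Section 6 schedule (also 12 months) into agreement. The choice of interval is the sponsor's.

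The cost is an amendment to wording plus, for each additional woman tested, up to five hCG assays (baseline and months 3, 6, 9 and 12). Blood is already drawn at all five visits, so no extra visit is needed. Sample size and analysis do not change.

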4.5 Subject Recruitment and Screening

4.5.1 Recruitment and Screening

Subject recruitment and screening will be conducted by members of the research team.

- Potentially eligible patients will be identified from the investigators' confidential clinical registry and referring physicians including self-referring patients
- If necessary, potential eligible patients will be recruited via online platform (i.e. Obesity Help, Bariatric Pal, Facebook), newspaper advertisements, study fliers, or study brochures
- In addition to these methods, subjects may be recruited through MyChart (if indicated they are willing to be contacted regarding research), DataCore, i2b2 or iConnect.
- DataCore may be used as a recruitment method to request reports from Epic, NYU's electronic medical record system. The following data points will be requested: medical record number (MRN), DOB (to assess current age), diagnosis, gender, and living status (alive). Patients will be contacted either by phone or e-mail by members of the research team using an IRB approved script. SendSafe Secure email will be used when sending these recruitment e-mails. Once contact is made, approved recruitment language will be used to communicate the reason they are being contacted and subjects will be asked if they are interested in participating in this specific study. If the potential subjects agree, the study team will provide the subjects with information regarding the next steps for participation. If a subject is ineligible or chooses not to participate their information will be deleted from the list immediately. PHI, including name, MRN, and DOB of patients who schedule an appointment will be kept on secure NYU servers. This information will be deleted if patients do not sign an informed consent form during their first visit. If a subject requests information regarding opting out of further recruitment for all research, subjects will be directed to contact study coordinator or have subjects contact [contact] or [name]. The amount of times EPIC will be searched over the

- course of the study will be dependent on the success of the results. We prefer to contact patients who are open for recruitment (based on their choice listed in Epic) directly.
 - Due to the time-sensitive inclusion criteria for this study (surgery between 18 months and 10 years), eligible participants may not have a treating physician on record in Epic as they may not have continued their care at NYUMC during this time. If they do have a primary care physician listed, the study team will notify the provider through their NYUMC email address using an IRB approved script stating that they are planning to contact this patient as indicated through a DataCore search and provide the PI and study team contact information if there are any concerns. If there is no primary care physician listed, this will be noted in the patient's research record; however they still may be contacted for research purposes.
 - The following roles will have access to the EPIC search results: Principle Investigator, Research Coordinator and Study Team Member.
 - The research staff will contact the potential patients via email or telephone if the contact information was sent to us via recruiting websites or the patients will contact the research staff directly using the contact information on the online websites.
 - Study eligibility will be determined by assessing evidence that the patient meets all inclusion and exclusion criteria
 - Patients will be offered the opportunity to participate in this study via telephone, email, mail or/and in-person conversation in a private room to protect patient's privacy. More privacy will be provided if required or demanded
 - A verbal explanation of the study will be given followed by a written consent form
 - For any patient who might be illiterate, consent forms will be read to him or her and witnessed by an impartial third party Patients will be provided with ample time and opportunity to ask about the details of the study, and decide whether or not they want to participate, and patient informed consent will be obtained, prior to any study specific procedures
 - No screening tests/procedures will be performed before a subject signs the consent form

4.5.2 Informed Consent

The purpose, procedures, risks, benefits, and alternatives to study participation will be discussed with each potential subject. The subject must also give Authorization for Use and Release of Health and Research Study Information and other written documentation in accordance with the relevant country and local privacy requirements (where applicable) prior to any study-related procedures or change in treatment.

The Investigator or his/her authorized designee conducts the informed consent (IC) discussion and will document in the subject's medical records the acquisition of IC and the subject's agreement. The IC shall include all aspects of the study that are relevant to the subject's decision to participate throughout the study. The IC process should avoid any coercion or undue influence on, or inducement of, the subject to participate. The subject should personally sign and date the IC form. The Investigator will retain the original copy of the signed form, and the subject will receive a copy. Upon signing the IC form, the subject is considered to be enrolled in the study and receives a subject number that will be used on all documentation for the subject throughout the study. The Investigator will ensure that important new information is provided to new or existing subjects throughout the study.

4.6 Early Withdrawal of Subjects

4.6.1 When and How to Withdraw Subjects

- If a subject is not able to tolerate the study drug, the subject will be removed from the study.
- If a subject decides to withdraw from the study, the subject will be removed from the study.

- If the PI believes that it is in a subject's best interest to discontinue participation, the subject will be removed from all remaining study requirements.
 - A subject may be withdrawn from the study at the discretion of the PI due to a safety concern or if judged non-compliant with trial procedures.

If a subject fails to return for one scheduled study visits, the Investigator will attempt to contact the subject to determine and document the reason the subject has failed to return and to encourage compliance with the study visit schedule. Before a subject can be considered lost to follow-up, a minimum of 2 phone calls at different times of the day and a certified letter are required. All of these contact attempts will be documented in the source documents.

In case of withdrawal from the study, the appropriate follow-up care will be provided for those cases, including hospital and clinic follow-up when necessary.

